11.2 Measurement

Cost measures

Total costs will be estimated using a bottom-up (or micro-costing) approach, where information on each element of service used is multiplied by an appropriate unit cost and summed to provide an overall total cost (32). We will assess intervention costs, healthcare costs, patient and family costs, and costs outside the health care sector. For this study we developed a cost questionnaire especially designed for this group, based on existing questionnaires, which will identify all relevant costs aspects (33;34).

To measure the actual use of resources data will be obtained using combined sources (registrations by professionals and cost questionnaire). Resources used relating to the interventions will be based on the registered time all professionals spent on the treatment. Intervention costs will include all the costs that will contribute to the procedure of ONS. All use of resources by the patient and their family in and outside the health care sector, will be measured by means of an interview by telephone, in which they are being asked about volumes of resource utilization 6 months retrospectively at baseline and at 6 months follow up. Cluster headache medication use will be registered in the electronic diary. These 2 sources of information will be combined.

The valuation of healthcare costs, patient and family costs will be based on the updated Dutch manual for cost analysis in healthcare research (35;36). This manual recommends using standardized cost prices. In brief, the manual recommends that prices of informal care will be based on shadow prices for unpaid work (meaning a standard cost price based on general hourly wages). Costs of medication will be calculated using prices taken from the Dutch Pharmacotherapeutic Compass (37). Productivity costs will be calculated by means of the friction cost method, based on a mean added value of the Dutch working population. The friction costs method takes into account production losses confined to the period needed (usually 90 days) to replace a sick employee. In case of uncertainty we will use a conservative estimation

Protocol: Occipital nerve stimulation in medically intractable, chronic cluster headache CME Protocol number: 10.016 Version 1.11 dd. 26-09-2018 (i.e. the lowest cost price). Cost prices will be expressed in 2009 euro's. If necessary, existing cost-prices will be updated to 2011 using the consumer price index (CPI) (35;36).

Outcome measures

The primary outcome measure for the cost-effectiveness analysis will be increase in health status as measured by the CH attacks 4-weekly at 6 months of follow-up of the last month of both treatment arms. Within the cost-utility analysis, utilities will be derived using an indirect preference-based technique. In this technique, the patient's health status will be monthly measured by means of the standard Dutch version of SF-36 and weights, that incorporate preferences from a general population sample, will be used to calculate utilities from the SF-36; the Short Form 6D (SF-6D) (29;31). The SF-36 will be completed monthly in the electronic diary and the cost questionnaire will be completed at baseline and at 6 months follow-up by an interview by telephone. The SF-36 is chosen because it is a widely used quality of life instrument (nationally and internationally), also in the field of headache (38). Utility values can be calculated for these health states, using preferences elicited from a general population, the socalled Brazier algorithm (29). The utility values derived from the Brazier algorithm will be used to compute QALYs. The Brazier algorithm has been established using a general population from the UK (29). The utilities at the time points will be used to compute a QALY score by means of the area under the curve method.

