11.1 Design and participants

Economic evaluations compare additional costs and additional outcomes of high stimulation compared to low stimulation. This economic evaluation will involve a combination of a cost-effectiveness analysis (CEA) and a cost-utility analysis (CUA). In a CEA effects are presented in clinical outcomes (in our study frequency of CH attacks during the last 4 weeks of the 100% stimulation period and the 30% stimulation period). The primary outcome measure for the cost-utility analysis will be Quality Adjusted Life Years (QALYs), based on the SF-36 utility scores (29-31). In the CUA, the Incremental cost-effectiveness ratio (ICER) will be expressed as the incremental costs per QALY. This economic evaluation will be performed from a societal perspective, which implies that all relevant costs and outcomes will be taken into account. With regard to this research question we hypothesize that the high stimulation is associated with an increased effect, and an increase in quality of life. The time horizon will be the same period as the follow-up period of the double blind part of the main study, 6 months. Costs (the use of resources) will be measured continuously using a (retrospective) questionnaire (6 months); outcomes for the economic evaluation study will be measured at pre-test before random assignment into groups (baseline), and at 6 months.

The second part of this economic evaluation will be a cost-of-illness (COI) study. The objective of this COI analysis is to calculate the societal costs of MICCH in the Netherlands. This prevalence based, retrospectively and bottom-up cost of illness Protocol: Occipital nerve stimulation in medically intractable, chronic cluster headache CME Protocol number: 10.016 Version 1.11 dd. 26-09-2018 study will be performed at baseline using a (retrospective) questionnaire (6 months) and an electronic diary for the use of attack medication.

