11.3 Analysis

No power calculations will be performed for the economic evaluation study as it is embedded in an RCT. Our primary (base-case analyses) will be performed according to the intention-to-treat principle, including data from all participants regardless of whether they received the intervention or not. For the analyses we will use SPSS statistical software and Excel database (for the Bootstraps).

To investigate whether data are normally distributed a Kolmogorov-Smirnov test will be performed. Despite the usual skewness in the distribution of costs, the arithmetic means will be generally considered the most appropriate measures to describe cost

data (39;40). Therefore arithmetic means (and standard deviations) will be presented. In case of skewness of the cost data, non-parametric bootstrapping will be used to test for statistical differences in costs between the 100% stimulation and the 30% stimulation group. Non-parametric bootstrapping is a method based on random sampling with replacement based on individual data of the participants (41). The bootstrap replications will be used to calculate 95% confidence intervals around the costs (95% CI), based on the 2.5th and 97.5th percentiles. If cost data are distributed normally, t-tests will be used.

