The ICER will be determined on the basis of incremental costs and effects of high stimulation compared to low stimulation. The cost-effectiveness ratio will be stated in terms of costs per outcome rate, the cost-utility ratio will focus on the net cost per QALY gained. The ICER will be calculated as follows. ICER = (Ci - Cc) / (Ei - Ec), where Ci is the annual total cost of the high stimulation group, Cc is the annual total cost of the low stimulation group, Ei is the effect at one year follow-up for the high stimulation group and Ec is the effect at one year follow-up for the low stimulation group. The robustness of the ICER will be checked by non-parametric bootstrapping (1000 times). Bootstrap simulations will also be conducted in order to quantify the uncertainty around the ICER, yielding information about the joint distribution of cost and effect differences. The bootstrapped cost-effectiveness ratios will be subsequently plotted in a cost-effectiveness plane, in which the vertical line reflects the difference in costs and the horizontal line reflects the difference in effectiveness. The choice of treatment depends on the maximum amount of money that society is prepared to pay for a gain in effectiveness, which is called the ceiling ratio. Therefore, the bootstrapped ICERs will also be depicted in a cost-effectiveness acceptability curve showing the probability that high stimulation is cost-effective using a range of ceiling ratios.

Additionally, to demonstrate the robustness of our base-case findings a multi-way sensitivity analyses will be performed. In the sensitivity analysis uncertain factors of assumptions in the base case analysis will recalculated in order to assess whether the assumptions have influenced the incremental cost-effectiveness ratio (ICER), for example by varying cost-prices and volumes between minimum and maximum (41).

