11.4 Cost-of-illness (COI)

The objective of this COI analysis is to calculate the societal costs of MICCH in the Netherlands. This prevalence based, retrospectively and bottom-up cost of illness study will be performed at baseline. Data for this COI will come from the baseline measurements of the a cost questionnaire especially designed for this group, based on existing questionnaires, which will identify all relevant costs aspects (33;34). The valuation of the COI will be based on the same methods as used in the economic evaluation (37).

12. Protocol deviations

Investigators are required to adhere to the Investigational Plan, signed Investigator's Agreement, applicable national or local, laws and regulations, and any conditions required by the appropriate Ethics Committees (EC) or applicable regulatory authorities.

Deviations from the protocol will not be permitted, except where necessary to protect the life or physical well-being of a patient in an emergency situation. If circumstances permit, the investigator should inform study management before initiating deviations. Prior notification is generally not expected in situations where unforeseen circumstances are beyond the investigator's control (e.g. patient did not attend scheduled follow-up visit). The investigator is required to adhere to the EC procedures for reporting deviations. Deviations include, but are not limited to the following:

- Failure to obtain informed consent prior to patient enrolment •
- Incorrect version of the informed consent form used •
- Enrolled patient did not meet the inclusion/exclusion criteria ٠
- Adverse Events not reported by investigators in the required timeframe as • specified in the protocol

Centre compliance with regard to deviations will be reviewed by the study coordinator on a timely basis. In addition, all deviations from the CIP will be documented in the final report.

13. Safety monitoring

The study investigators are responsible for the detection and documentation of adverse events (AEs) and device events.

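### Section 11 specifies no baseline adjustment of QALYs or costs, although baseline utility and baseline 6-month resource use are both collected; adding it is a free gain in precision

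*Combined protocol and SAP*

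**What the plan says.** **QALYs.** Section 11.2 derives SF-6D utilities from the SF-36 and states: "The utilities at the time points will be used to compute a QALY score by means of the area under the curve method". On timing, Section 11.1 says "outcomes for the economic evaluation study will be measured at pre-test before random assignment into groups (baseline), and at 6 months", while Section 11.2 says "The SF-36 will be completed monthly in the electronic diary".

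**Costs.** Resource use is obtained by telephone interview, as "volumes of resource utilization 6 months retrospectively at baseline and at 6 months follow up" (Section 11.2). Section 11.3 presents arithmetic means and, for skewed costs, says that "non-parametric bootstrapping will be used to test for statistical differences in costs between the 100% stimulation and the 30% stimulation group"; for normally distributed costs it names t-tests.

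**ICER.** Section 11.3: "The ICER will be determined on the basis of incremental costs and effects of high stimulation compared to low stimulation". The formula is the arm difference in cost divided by the arm difference in effect, bootstrapped 1000 times for the plane and the acceptability curve. The sensitivity analysis gives variation of prices and volumes as its example.

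**Use of the baseline data.** The one stated use of the baseline cost data is the cost-of-illness study: "Data for this COI will come from the baseline measurements of the a cost questionnaire especially designed for this group" (Section 11.4). Section 16.2 does adjust the clinical endpoint for its baseline (lnMAF0) and gives increased power as a reason, but that model covers attack frequency only.

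**The concern.** Baseline utility is the first point on each patient's curve, and utilities are likely to be correlated over time. If the arms differ at baseline by chance, the difference is carried into the area under the curve in two ways: arithmetically, through the weight of the first point, and through the later values that correlate with it. For costs only the second route exists, because the six months before baseline are not part of the follow-up total.

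The QALY difference is the denominator of the cost-utility ICER and can only be small over six months, so modest noise matters. Section 11.3 also states that the economic evaluation has no power calculation of its own, which makes avoidable variance more costly there. The plan already accepts the reasoning for its clinical endpoint in Section 16.2 but does not extend it to Section 11.

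**Working it through.** The plan gives no power, SD or correlation for utilities or costs, so it has no figure of its own to reproduce here.

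**Inputs from the documents**
- 144 patients in two equal arms, so 72 per arm; 20% drop-out (Section 16.4) leaves about 58 per arm (72 × 0.8 = 57.6).
- A month is 4 weeks (Section 7.1), so 6 months = 24 weeks = 24/52 = 0.46 year.
- Monthly utilities (Section 11.2), so seven values, month 0 to month 6.

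**Assumptions, not in the documents**
- SF-6D SD of 0.12 at every time.
- Either equal correlation r between all months, or AR1 with lag-1 correlation r; r = 0.4, 0.6, 0.8. AR1 is included because it is the plan's default for the repeated attack-frequency data (Section 16.5).
- A benchmark treatment effect: a utility gain of 0.04, rising linearly to month 2 and then held.

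**Step 1: size of an ordinary imbalance.** The standard error of the baseline difference is 0.12 × √(2/72) = 0.020.

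**Step 2: weights.** The trapezoid rule gives w = (0.5, 1, 1, 1, 1, 1, 0.5)/6, so baseline carries 1/12 of the area.

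**Step 3: carry-over.** The slope of the mean utility on baseline utility is Σ wⱼ·corr(u₀, uⱼ). Under equal correlation this is 1/12 + (11/12)r, which is 0.633 at r = 0.6. The shift in the QALY difference is slope × 0.02 × 0.46; at r = 0.6 it is 0.633 × 0.02 × 0.46 = 0.0058.

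**Step 4: benchmark.** (0.02 + 4 × 0.04 + 0.5 × 0.04)/6 × 0.46 = 0.0333 × 0.46 = 0.0154 QALY, or about 0.015.

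**Step 5: precision.** With R the correlation matrix, adjustment for baseline removes the fraction slope²/(w′Rw) of the variance. At equal correlation 0.6 this is 0.633²/0.661 = 0.61.

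| Structure | r | Slope | Shift for one-SE imbalance | Shift as share of 0.0154 | Variance removed | SEs of imbalance needed to cancel 0.0154 |
|---|---|---|---|---|---|---|
| Equal | 0.4 | 0.450 | 0.0042 | 27% | 41% | 3.7 |
| Equal | 0.6 | 0.633 | 0.0058 | 38% | 61% | 2.6 |
| Equal | 0.8 | 0.817 | 0.0075 | 49% | 80% | 2.0 |
| AR1 | 0.4 | 0.194 | 0.0018 | 12% | 12% | 8.6 |
| AR1 | 0.6 | 0.318 | 0.0029 | 19% | 22% | 5.2 |
| AR1 | 0.8 | 0.553 | 0.0051 | 33% | 46% | 3.0 |

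With 58 per arm and r = 0.6, the standard error of the QALY difference falls from 0.0084 to 0.0052 under equal correlation, and from 0.0069 to 0.0061 under AR1.

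**Step 6: if only baseline and 6 months are used**, as Section 11.1 can be read, baseline carries half of the area and the slope is (1 + r)/2. The one-SE shift is then 0.0065 to 0.0083 for r = 0.4 to 0.8, and the variance removed is (1 + r)/2, or 70 to 90%.

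**Step 7: costs.** Adjustment removes a fraction ρ² of the variance, where ρ is the correlation between baseline and follow-up cost. The documents give no ρ. Follow-up costs include the implantation procedure (Section 11.2), which baseline costs do not, so ρ cannot be presumed to be large. No figure is offered.

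**The case against.** Much of the case on the other side stands.

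- **Bias.** A reader might infer that the crude ICER is biased. It is not, in that sense: allocation is randomised and stratified (Section 16.6), so the crude cost and QALY differences are unbiased on average. The issue is error in the one sample obtained, and lost precision.
- **Sign reversal.** A reader might infer that ordinary imbalance could reverse the sign of the QALY difference. For a gain of about 0.015 QALY, the shift alone would have to come from an adverse imbalance of 2.0 to 3.7 standard errors under equal correlation, and 3.0 or more under AR1. That is not ordinary.
- **Correlation structure.** Equal correlation is favourable to adjustment, since it ties month 6 to baseline as closely as month 1. Under AR1 the gain is much smaller, so both ranges must be reported.
- **Costs.** The arithmetic route does not apply to them, and the gain is unknown.
- **Silence.** The plan does not rule adjustment out. It is silent, and the t-test and bootstrap comparison is named for costs rather than QALYs. Silence does, however, leave the choice open until the data have been seen, and every estimator that is named is a two-group one.
- **Scope.** The evaluation is a secondary, unpowered part of the trial. The cost-effectiveness ratio uses attacks as its effect, so the QALY argument does not touch that denominator.

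None of this gives a reason to leave collected baseline values unused.

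**Conclusion.** The point holds as a free improvement, not as an error that invalidates the economic evaluation. Section 11 names no baseline adjustment for QALYs or costs, although the needed values are collected and Section 16.2 applies the same idea to the clinical endpoint.

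Under the stated assumptions, a one-standard-error imbalance moves the QALY difference by 0.002 to 0.008 across the two correlation structures, against about 0.015 for the benchmark gain, and adjustment removes between 12% and 80% of its variance. The direction is secure: with equal SDs and positive correlation, the variance falls. The size is not, because the SD, the correlations and the benchmark gain are all assumed.

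Two conflicts in the text change the arithmetic and need reconciling in their own right: utilities monthly (Section 11.2) or at baseline and 6 months (Section 11.1), and a 6-month horizon (Section 11.1) against annual costs and one-year effects in the ICER formula (Section 11.3).

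**What to change.** In Section 11.3, specify that:

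1. Incremental QALYs are estimated by regression of the area under the curve on arm and baseline SF-6D utility. Section 9.1 lists a monthly SF-36 within the 12-week baseline diary, so several baseline values may exist. State in advance whether the covariate is the last pre-randomisation value or the mean of the baseline values.
2. Incremental costs are estimated by regression on arm and baseline 6-month cost.
3. Both regressions are fitted within each bootstrap replicate, on the same resampled patients, so that the correlation between costs and effects is kept.
4. The cost-utility ICER, the plane and the acceptability curve are built on the adjusted differences.

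The cost is SAP wording and analysis code. No new data, visits or patients are needed.

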11.3 Analysis

No power calculations will be performed for the economic evaluation study as it is embedded in an RCT. Our primary (base-case analyses) will be performed according to the intention-to-treat principle, including data from all participants regardless of whether they received the intervention or not. For the analyses we will use SPSS statistical software and Excel database (for the Bootstraps).

To investigate whether data are normally distributed a Kolmogorov-Smirnov test will be performed. Despite the usual skewness in the distribution of costs, the arithmetic means will be generally considered the most appropriate measures to describe cost

data (39;40). Therefore arithmetic means (and standard deviations) will be presented. In case of skewness of the cost data, non-parametric bootstrapping will be used to test for statistical differences in costs between the 100% stimulation and the 30% stimulation group. Non-parametric bootstrapping is a method based on random sampling with replacement based on individual data of the participants (41). The bootstrap replications will be used to calculate 95% confidence intervals around the costs (95% CI), based on the 2.5th and 97.5th percentiles. If cost data are distributed normally, t-tests will be used.

The ICER will be determined on the basis of incremental costs and effects of high stimulation compared to low stimulation. The cost-effectiveness ratio will be stated in terms of costs per outcome rate, the cost-utility ratio will focus on the net cost per QALY gained. The ICER will be calculated as follows. ICER = (Ci - Cc) / (Ei - Ec), where Ci is the annual total cost of the high stimulation group, Cc is the annual total cost of the low stimulation group, Ei is the effect at one year follow-up for the high stimulation group and Ec is the effect at one year follow-up for the low stimulation group. The robustness of the ICER will be checked by non-parametric bootstrapping (1000 times). Bootstrap simulations will also be conducted in order to quantify the uncertainty around the ICER, yielding information about the joint distribution of cost and effect differences. The bootstrapped cost-effectiveness ratios will be subsequently plotted in a cost-effectiveness plane, in which the vertical line reflects the difference in costs and the horizontal line reflects the difference in effectiveness. The choice of treatment depends on the maximum amount of money that society is prepared to pay for a gain in effectiveness, which is called the ceiling ratio. Therefore, the bootstrapped ICERs will also be depicted in a cost-effectiveness acceptability curve showing the probability that high stimulation is cost-effective using a range of ceiling ratios.

Additionally, to demonstrate the robustness of our base-case findings a multi-way sensitivity analyses will be performed. In the sensitivity analysis uncertain factors of assumptions in the base case analysis will recalculated in order to assess whether the assumptions have influenced the incremental cost-effectiveness ratio (ICER), for example by varying cost-prices and volumes between minimum and maximum (41).

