9.2 Schedule

Visit 1: study neurologist: inclusion/exclusion criteria

Visit 2: visit neurosurgeon (or implanter)/investigator: information about the surgery and study: reflection period of 7-14 days (or as long the patients needs)

Visit 3: informed consent study neurologist. Start electronic diary

Visit 4: anaesthesiologist

Evaluation headache diary by study coordinator: does the patient still meet inclusion criteria: at least 4 attacks per week?

Interview by telephone (medical student): economic evaluation questionnaire

Randomisation

Visit 5: surgery and defining stimulation parameters: 2-3 days in hospital

Visit 6: **+10 days** control of wound and removal of stitches **t=0** and calibration of stimulation

Visit 7: + 1 month: checking and changing of stimulation follow-up

Visit 8: + 2 months checking and changing of stimulation follow-up

Visit 9: + 4 months: checking of stimulation follow-up

Interview by telephone (student) after 6 months: economic evaluation questionnaire

Visit 10: + 6 months: checking of stimulation follow-up

Plus monthly visits study neurologist (an exception will be made for the visits at 3 and 5 months follow-up, because in case the participating patient prefers a telephone call instead, this will be allowed)

Open trial:

Visit 11: +9 months: checking of stimulation follow-up

Visit 12: + 12 months: checking of stimulation follow-up

Plus three-monthly visit study neurologist

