9.3 Interview by telephone

The patient will be interviewed by telephone twice by a medical student to answer a questionnaire about health consumption and absenteeism.

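### Section 11.3 defines the ICER on annual costs and one-year effects, but the economic evaluation is set up for the 6-month blinded phase

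*Combined protocol and SAP*

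**What the plan says.** Section 11.3 gives the ICER as (Ci - Cc) / (Ei - Ec) and defines the terms on a one-year basis: "Ci is the annual total cost of the high stimulation group, Cc is the annual total cost of the low stimulation group", and "Ei is the effect at one year follow-up for the high stimulation group", with Ec defined likewise for the low arm.

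The rest of the economic plan is on a 6-month basis:

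- Section 11.1, horizon: "The time horizon will be the same period as the follow-up period of the double blind part of the main study, 6 months".
- Section 11.1, timing of outcomes: "outcomes for the economic evaluation study will be measured at pre-test before random assignment into groups (baseline), and at 6 months".
- Section 11.2, cost-effectiveness outcome: "the CH attacks 4-weekly at 6 months of follow-up of the last month of both treatment arms".
- Section 11.2, costs: "the cost questionnaire will be completed at baseline and at 6 months follow-up by an interview by telephone". The same section gives each interview a 6-month look-back.
- Section 9.3: "The patient will be interviewed by telephone twice by a medical student to answer a questionnaire about health consumption and absenteeism". Section 9.2 places the second of these at month 6 ("Interview by telephone (student) after 6 months: economic evaluation questionnaire") and lists none at month 9 or 12.

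Section 11 states the objective as a comparison of 100% with 30% stimulation from a societal perspective. Section 4 has every patient move, after the 6 blinded months, to 100% or to the level the patient judges best.

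**The concern.** An analyst would program the formula in Section 11.3, and it does not answer the question posed at the start of Section 11. Three things are at stake.

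1. **The comparison changes.** No 30% arm is maintained after month 6. A one-year contrast by randomised arm describes early against delayed access to open stimulation, which the plan does not state as an objective.
2. **Part of the cost is not observed.** A societal perspective needs all relevant costs. For months 6-12 the diary continues with medication use and absenteeism (Sections 4 and 9.6), and intervention costs come from professionals' registered time (Section 11.2). Other health-care use and patient and family costs have no stated source after the month-6 interview.
3. **The horizon is left open.** With two time bases in the plan, the choice between them could be made after the data are seen.

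**Working it through.** The plan states no ICER, cost or QALY figure and rules out a power calculation for this part, so there is no figure to reproduce. The check is a comparison of the text, followed by arithmetic showing how much the time basis can matter.

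**Can the two time bases be read as one?** Taking annual to mean annualised (6-month cost doubled) leaves the one-year effect terms unexplained. Taking it as the two 6-month recall windows added together would mix pre-randomisation cost into the comparison, and still would not match an effect at one year. No section calls the one-year ICER secondary or says how month 6-12 costs would be obtained.

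**Inputs from the documents.** Expected change from baseline is -9 attacks per week at 100% and none at 30% (Section 16.4). The high arm receives 100% for 4 months of the blinded phase (Section 4).

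**Exposure to the full contrast.** 4/6 = 67% of the blinded phase, but 4/12 = 33% of a year. These shares describe the comparison and do not enter the ratios below.

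**Assumptions.** Let c, from 0 to 1, be the share of the month-6 between-arm difference that remains at one year. The documents do not give it. Let u be a constant utility gap in months 0-6, falling to cu in months 6-12. The constant gap is a simplification, because stimulation is stepped up first.

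**Cost-effectiveness (attacks).** The planned difference is 9 x 4 = 36 attacks per 4 weeks, so the one-year denominator is 36c. Relative to the 6-month ICER:

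- with the same cost difference, the multiplier is 1/c;
- if the month 6-12 cost difference is c times that of months 0-6, the annual cost difference is (1 + c) times the 6-month one, and the multiplier is (1 + c)/c.

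**Cost-utility (QALYs).** The 12-month QALY difference is 0.5u + 0.5cu = u(1 + c)/2. The 6-month difference is 0.5u. Relative to the 6-month ICER:

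- with the same cost difference, the multiplier is 0.5u / [u(1 + c)/2] = 1/(1 + c);
- if the cost difference also scales by (1 + c), the multiplier is 1 for every c.

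| c | Attack difference per 4 weeks, 36c | CEA multiplier, same cost difference | CEA multiplier, cost difference x (1 + c) | 12-month QALY difference, % of u | CUA multiplier, same cost difference |
|---|---|---|---|---|---|
| 1 | 36 | 1 | 2 | 100% | 0.50 |
| 0.75 | 27 | 1.33 | 2.33 | 87.5% | 0.57 |
| 0.5 | 18 | 2 | 3 | 75% | 0.67 |
| 0.25 | 9 | 4 | 5 | 62.5% | 0.80 |
| 0 | 0 | undefined | undefined | 50% | 1 |

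**Mixing the two bases.** Assume a utility gap of 0.05 to 0.10 and a cost difference of 1,000 euro per 6 months, neither of which is in the documents. The 6-month ICER is 1,000/(0.05 x 0.5) = 40,000 down to 1,000/(0.10 x 0.5) = 20,000 euro per QALY. Annual (doubled) costs over the 6-month QALY difference give 80,000 down to 40,000. With both terms over 12 months and the contrast persisting, the ratio returns to 40,000 down to 20,000.

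**The case against.** The strongest reply is that this is a drafting slip. Only Section 11.1 uses the term time horizon, and the outcome, the questionnaire timing, the number of interviews and the visit schedule all agree with it. Against them stands one run of symbol definitions, possibly carried over from a template, in a secondary and unpowered analysis. Since a full one-year societal cost cannot be built from the planned data, the room to choose the horizon later is limited.

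Much of this is fair and bounds the importance of the point. It does not remove the contradiction, because the outlying text is the formula itself.

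Four narrower objections also have weight:

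- The diary runs throughout the study and includes attack frequency and a monthly SF-36, so one-year effects and QALYs look computable. The data gap is confined to other health-care and patient and family costs.
- The multipliers depend on an assumed c. The factor of 2 at c = 1 arises only because a 12-month cost is divided by a 4-week attack rate.
- The cost-utility ratio can be unchanged, or can move in the opposite direction from the attack-based ratio, as the table shows.
- Early against delayed 100% stimulation could be a legitimate question, but the plan neither poses it nor collects full costs for it.

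**Conclusion.** The concern holds. Section 11.3 states the ICER on a time basis that contradicts Sections 11.1, 11.2, 9.2 and 9.3. Followed literally, it estimates a comparison other than the stated one, on incomplete costs.

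The size is illustrative, since it rests on the assumed c and on how cost differences develop after month 6. The attack-based ratio is most exposed: with an unchanged cost difference it doubles at c = 0.5, quadruples at c = 0.25, and has no defined value if the arms converge fully. The QALY difference does not vanish even then, and the cost-utility ratio is unchanged if costs and utilities scale together. It moves when costs are front-loaded or only partly observed.

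The primary endpoint, its analysis and the sample size are not affected. This should be corrected, at the level of a secondary analysis.

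**What to change.** In Section 11.3:

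- Define Ci and Cc as total cost per arm over the 6-month double-blind phase.
- Define Ei and Ec as the 4-weekly attack frequency at month 6 for the cost-effectiveness analysis, and as QALYs over months 0-6 from the monthly SF-6D for the cost-utility analysis.
- State one time origin for both costs and QALYs. Section 9.6 counts months from randomisation, the follow-up table in Section 4 counts from surgery, and Section 9.2 labels the 10-day visit as t=0.
- Present any one-year result by arm only as a description of the open phase.

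In Section 11.1, align the statement that outcomes are taken at baseline and 6 months with the monthly SF-36 in Section 11.2, which the area-under-the-curve calculation uses.

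The cost is a wording change in Sections 11.1 and 11.3, with no new data. The trial gives up a nominal one-year ICER by arm.

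A separate and minor improvement, not needed to resolve the contradiction, is to estimate incremental QALYs by regression on baseline utility within the bootstrap. This removes chance baseline imbalance and gains precision.
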